# Endpoint(s)

- Proportion and frequency of preservative free artificial tears use (n° drops/day) during the treatment period.
- Frequency of preservative free artificial tears use (n° drops/day) during the follow-up period.
- Change from baseline in Schirmer I test (without anesthesia) Vs week 2.
- Change from baseline in SANDE global scores, and for severity and frequency [Time frame: week 2 and 4].
- Change from baseline in Cornea and conjunctiva vital staining with fluorescein (NEI scale) Vs week 2.
- Change from baseline in TFBUT Vs week 2.
- Number of patients experienced a worsening in symptom scores (SANDE global score) and/or NEI score ≥ 50% assessed at week 2.

| Objective(s)  | Endpoint(s)   |
|---|---|
| • To compare the efficacy of cenegermin vs. vehicle in Schirmer II test at week 4 by testing the superiority. | • Change from baseline Schimer test II (with topical Anesthesia) vs Week 4. |
| • To evaluate the Best Corrected Distance
Visual Acuity (BCDVA) throughout the
study.                   | • Change from baseline in BCDVA.  |
| 3.2.4 Safety  |   |
| Objective(s)  | Endpoint(s)   |
| • To evaluate the safety and tolerability of cenegermin vs. vehicle, as measured by                           | • Incidence and frequency of TEAEs, assessed throughout the study.          |

# 3.3 Schedule of evaluations

(TEAEs).

Treatment-Emergent Adverse Events

During the screening (day-8) all procedures for inclusion will be performed. From the day of screening the patients will stop any kind of further treatment, except CsA and commercially available preservative free artificial tears provided by Sponsor for a period of 8 days and 10 days as maximum: day -8 until the baseline visit (day 1+2). At the end of the wash out period (day -8 to baseline), patients meeting the entry criteria for this study will be randomized 1:1 and treated for 4 weeks with either cenegermin ophthalmic solution 20 mcg/mL TID or vehicle TID.

In addition to topical CsA eye drops (both groups will continue with topical CsA eye drops, or other topical ophthalmic treatment of the same class, as previously prescribed), during the 4 weeks of masked treatment only the administration of IMP is allowed. Nevertheless, if strictly needed, the patient can take preservative free artificial tears (provided by the Sponsor). The use (n° drops/day) of preservative free artificial tears will be clearly documented in a patient's diary and in the eCRF.

Eight weeks post treatment with no further topical ocular treatment except CsA and commercially available preservative-free artificial tears provided by the Sponsor TID will follow the completion of the double-blind treatment. During this follow up period, the patient can administer additional preservative-free artificial tear eye drops, provided by Sponsor, only if strictly needed, and must document in the patient's diary the number of additional drops administered for each eye.

Patients will then be followed up for efficacy and safety endpoints until week 16 and for safety endpoints until week 24. During the follow up period after week 12 until week 24 other topical treatments, in addition to CsA, will be allowed at discretion of the treating physician. Such treatments will be recorded by the investigators.

Throughout the study, the patient can continue any systemic treatment as required to control their autoimmune disease, and any change in systemic treatments must be recorded by the investigators.

The total duration of the study is 25 weeks including 1 week of screening.

#### Figure 1: Study duration

#### 4. General definitions

#### 4.1 Investigational drug and study treatment

Oxervate®, an ophthalmic solution containing cenegermin 20 mcg/mL, which is a recombinant human Nerve Growth Factor (rhNGF); reference product is vehicle. Test and reference will be instilled in both eyes for 28 consecutive days according to the following scheme:

- Group 1: one drop of cenegermin 20 mcg/mL will be instilled in both eyes TID (every 6 hours, e.g. 7:00 am, 01:00 pm; 07:00 pm).
- Group 2: one drop of vehicle will be instilled in both eyes TID (every 6 hours, e.g. 7:00 am, 01:00 pm; 07:00 pm).

Both groups will continue with topical CsA eye drops (or other topical ophthalmic treatment of the same class) as previously prescribed at least 15 minutes apart. The IMP will be provided in a monthly box containing 28 daily vials. Together with the IMP monthly box, patients will be provided with a sufficient number of pipettes and adaptors for the administration of the IMP.

#### 4.2 Date of first and last administration of study drug

The date of first administration of study drug is defined as the baseline date.

The date/time of last administration of study drug is defined as the Date of last treatment administration as per End of treatment eCRF form. This value has to be consistent with IMP Administration information recorded on the corresponding eCRF forms. In case of different dates, the latest will be used as treatment end.

#### 4.3 Study day

The study day describes the day of the event or assessment date, relative to the reference start date which is the date of Visit 1 - Baseline.

The study day is defined as:

- The date of the event (visit date, onset date of an event, assessment date etc.) reference start date + 1 if event is on or after the reference start date.
- The date of the event (visit date, onset date of an event, assessment date etc.) reference start date if event precedes the reference start date.

# 4.4 Visit Schedule and Visit Windows

Assessments and study visits will be performed as listed in Paragraph no. 2 ("Schedule of evaluations") and in Paragraphs no. 6 ("Study Procedure and Assessments") of the Study Protocol [1] containing additional details about scheduled visits and time windows.

Scheduled visits and time windows are:

- Screening (Day -8)
- Visit 1 Baseline (Day 1 + 2 days)
- Visit 2 Week 2 (Day  $14 \pm 2$  days)
- Visit 3 End of treatment Week 4 (Day  $28 \pm 2$  days)
- Visit 4 follow-up Week 8 (Day  $56 \pm 2$  days)
- Visit 5 follow-up Week 12 (Day  $84 \pm 4$  days)
- Visit 6 follow-up Week 16 (Day  $112 \pm 7$  days)
- Visit 7 follow-up Week 24 (Day  $168 \pm 7 \text{ days}$ )

For efficacy and safety endpoints, data will be evaluated according to the Visit at which they have been collected.

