- **10.** Any concurrent medical condition, that in the judgment of the PI, might interfere with the conduct of the study, confound the interpretation of the study results, or endanger the patient's well-being
- **11.** Use of topical corticosteroids, lifitegrast, autologous serum tears in either eye during the study (previous use not an exclusion criteria but must be discontinued at the screening visit)
- **12.** Contact lenses, True Tear device, moisture goggles, sutureless amniotic membrane or punctum plug use during the study (previous use not an exclusion criteria but must be discontinued at the screening visit)
- **13.** History of drug addiction or alcohol abuse within the last year
- **14.** Any prior ocular surgery (including refractive, palpebral and cataract surgery) if within 90 days before the screening visit
- **15.** Participation in a clinical trial with a new active substance during the past 3 months prior to screening
- 16. Participation in another clinical trial study at the same time as the present study

Test/Reference Product,	Oxervate ® , an ophthalmic solution containing cenegermin 20
Dosage and Mode of	mcg/mL, which is a recombinant human Nerve Growth
Administration	Factor (rhNGF); reference product is vehicle. Test and
Duration of treatment	reference will be instilled in both eyes for 28 consecutive days according to the following scheme:
	Group 1: one drop of cenegermin 20 mcg/mL will be instilled in both eyes TID (every 6 hours, e.g. 7:00 am, 01:00 pm; 07:00 pm).
	Group 2: one drop of vehicle will be instilled in both eyes TID (every 6 hours, e.g. 7:00 am, 01:00 pm; 07:00 pm).
	Both groups will continue with topical CsA eye drops (or other topical ophthalmic treatment of the same class) as previously prescribed at least 15 minutes apart. The investigational medicinal Product (IMP) will be provided in a monthly box containing 28 daily vials. Together with the IMP monthly box, patients will be provided with a sufficient number of pipettes and adaptors for the administration of the IMP.
Study procedures	Patients will be evaluated at screening (day -8), baseline (day 1+2), and week 2 (day 14 $\pm$ 2), week 4 (day 28 $\pm$ 2) or early exit, week 8 (day 56 $\pm$ 2), week 12 (day 84 $\pm$ 4), and week 16 (day 112 $\pm$ 7) follow-up visits. Safety evaluations will continue until week 24 (day 168 $\pm$ 7) Screening Visit (day -8): all tests/measurements for assessment of eligibility will be performed.

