Visit 6 Follow up week 16	Day 112 ± 7	
 
The following procedures will be performed (the below order is mandatory):
 
Pregnancy test for female patients of childbirth potential
 
Ocular examination of both eyes to be performed by the physician investigator: 
 
Assessment by SANDE questionnaire
 
Assessment of best corrected distance visual acuity (BCDVA)
 
External Ocular Examination
 
Schirmer test I (without anesthesia)
 
Slit-lamp examination (SLE) to assess the Eyelid - Meibomian glands, Eyelid 
 
Erythema, Eyelid - Edema Lashes, Conjunctiva Erythema, Lens, Iris, Anterior Chamber, Corneal Horizontal Diameter
 
 
 
TFBUT
 
Ocular surface staining (NEI score - corneal and conjunctival fluorescein staining)
 
Concomitant ocular and systemic medication
 
Frequency of patient's artificial tear use during 4 weeks of FU (to be reported in cCRF)
 
AE monitoring
 
 
 
PI or delegate must check the patient's diary concerning the previous follow up period.
 

Visit 7 Follow up week 24 Final visit or early termination visit (ETV)	Day 168 ± 7	
 
The End of Study (EoS) visit is defined as the last follow-up at week 24. In case of premature study discontinuation, patients will undergo an Early Termination Visit (ETV).
 
Concomitant ocular and systemic medication
 
Frequency of patient's artificial tear use during 8 weeks of FU (to be reported in eCRF)
 
AE monitoring
 
PI or delegate must check and collect the patient's diary concerning the last follow up period.
 

---	-------------	---

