## 6.3.2. Discontinuation procedures

### Treatment discontinuation

Patients who discontinue the treatment will not be withdrawn from the study by default, but will be asked to complete safety and efficacy observations as per the protocol, unless otherwise they withdraw their consent.

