#### **Study discontinuation**

For any patient discontinuing the study following randomization, the Investigator will:

- ask the patient to undergo, as far as possible, a final medical visit (Early Termination Visit ETV) to examine the patient's health conditions. This examination will verify that all values tested at screening have remained within a clinically acceptable range (i.e., not clinically significant changes compared to screening).
- > arrange for alternative medical care of the withdrawn patient, if necessary.
- report in the eCRF date and time of the last dose administration, and date and primary reason of study discontinuation.
- record in the eCRF any follow-up if the patient is withdrawn for an AE. AE's should be followed until resolution.

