# 7.3 Primary estimand

The primary endpoints will be analyzed using treatment policy estimands, defined by the following:

Primary endpoint:

- Population: Adult patients with severe Sjogren's dry eye disease under treatment with Cyclosporine A, as defined by the inclusion-exclusion criteria of the study (and matching the FAS definition);
- Variable: Schirmer I test at week 4;
- Intercurrent event: The occurrence of an intercurrent event is irrelevant. All observed values will be used regardless of occurrence of an intercurrent event. Retrieved drop-outs will be used for data imputation of missing data;
- Population-level summary: Difference in proportion of patients reaching a value of Schirmer I test (without anesthesia) >10mm/5min at week 4.

Coprimary endpoint:

- Population: Adult patients with severe Sjogren's dry eye disease under treatment with Cyclosporine A, as defined by the inclusion-exclusion criteria of the study (and matching the FAS definition);
- Variable: SANDE global score at week 12;

- Intercurrent event: The occurrence of an intercurrent event is irrelevant. All observed values will be used regardless of occurrence of an intercurrent event. Retrieved drop-outs will be used for data imputation of missing data;
- Population-level summary: Difference in means of change from baseline in the global SANDE score at week 12.

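### The protocol is inconsistent about where early-exit data are recorded and SAP 4.4 does not resolve it, so a Schirmer value taken before day 26 may be analysed as an observed week-4 co-primary result

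*SAP*

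**What the plan says.** **SAP.** Section 4.4 refers to Protocol sections 2 and 6 for the visits and lists the visit windows. The entry "Visit 3 End of treatment Week 4" has a window of day 28 ± 2, that is day 26 to 30, and does not mention early exit. The windows are then not used to assign data: "For efficacy and safety endpoints, data will be evaluated according to the Visit at which they have been collected". Sections 7.8 (missing data) and 7.9 (changes from the protocol) add no rule for early-termination or out-of-window values. The estimand in 7.3 has "Variable: Schirmer I test at week 4". Under 10.1.2.1, monotone missing Schirmer values are imputed from retrieved drop-outs (MI-RD), or by Copy Reference if there are too few of them.

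**Protocol: early exit joined to week 4.** The synopsis (Study procedures) lists "week 4 (day 28 $\pm$ 2) or early exit". The interventional-phase list in section 6 does the same.

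**Protocol: early exit placed elsewhere.** The visit table in 6.2 has the row "Visit 7 Follow up week 24 Final visit or early termination visit (ETV"). It lists medications, artificial-tear use, adverse events and the diary, but no Schirmer test. For patients who leave the study, 6.3.2 tells the investigator to "ask the patient to undergo, as far as possible, a final medical visit (Early Termination Visit ETV) to examine the patient's health conditions". It adds: "This examination will verify that all values tested at screening have remained within a clinically acceptable range". Screening includes Schirmer I. The schedule in section 2 and the detailed Visit 3 procedures in 6.2 give day 28 ± 2 only.

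**Stopping treatment only.** Section 6.3.2 says: "Patients who discontinue the treatment will not be withdrawn from the study by default". These patients stay on the assessment schedule.

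**The concern.** A purely nominal visit rule is safe only if the visit label fixes the time of measurement. Here two protocol entries let one label cover both day 28 and an exit on any earlier day. If an exit examination is entered under that label, SAP 4.4 makes its Schirmer result the week-4 endpoint. Another protocol passage would leave the same patient missing at week 4.

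Such exits are foreseen and can be related to outcome. Protocol 6.3.1 names insufficient response or worsening after two weeks of treatment as a reason for leaving the study, and 3.3.1 allows discontinuation at any time.

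What is at stake is whether a confirmatory co-primary endpoint measures what the estimand names. A treatment-policy strategy says that intercurrent events do not remove observed week-4 values. It does not turn an earlier value into a week-4 value. The week-4 tests of IDEEL, NEI staining and TFBUT in the key secondary hierarchy, and the week-4 worsening endpoint, share the ambiguity.

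**Working it through.** **1. The plan's own figure.** Inputs from SAP section 5: vehicle 33%, difference 42 points (so cenegermin 75%), 36 evaluable per arm, one-sided alpha 0.025. Pooled-variance formula for two proportions, with mean rate 0.54:

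- null SE = √(2 × 0.54 × 0.46 / 36) = 0.1175
- alternative SE = √((0.33 × 0.67 + 0.75 × 0.25) / 36) = 0.1065
- power = Φ((0.42 − 1.96 × 0.1175) / 0.1065) = Φ(1.78) = 96.3%

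This matches the stated 96.3%. The sample-size figures are not in question; they supply the rates used in step 4.

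**2. One patient followed through the text.** Take a patient who leaves the study on day 10 and has a Schirmer test at the exit examination.

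| Step | Recorded as the week-4 visit (synopsis, section 6 list) | Recorded as Visit 7 or a separate ETV (6.2 table, 6.3.2) |
|---|---|---|
| Week-4 status under SAP 4.4 | Observed | Missing |
| MI-RD or Copy Reference (10.1.2.1) | Not applied | Applied |
| Tipping point (10.1.3), which shifts only imputed cenegermin values | Value not shifted | Shifted if in the cenegermin arm |
| Complete-case analysis (10.1.4), which drops only missing endpoints | Kept | Dropped |

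**3. Donor role.** SAP 10.1.2 defines retrieved drop-outs as patients who stop treatment but remain in the study. The code in 15.4.1 selects donors only by EOTSTT being NOT COMPLETED. I read this as treatment status; the SAP does not define the variable. On the week-4 route, an early exit with a filled week-4 value meets the code's condition but not the text's definition. It could then inform the imputation of other patients. Where true retrieved drop-outs are few, it could also influence whether MI-RD converges and so which method is used.

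**4. Size.** Protocol 4.4 gives about 40 patients per arm. One patient classified as responder rather than non-responder moves that arm's rate by 1/40 = 2.5 points at most. This counts the patient's own value, not any effect as a donor.

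To show the possible directions, assume that m = 4 cenegermin patients (10% of 40) exit before day 26, that all have a recorded Schirmer value, that the other 36 respond at 75% and that vehicle responds at 33%. The cenegermin rate is 0.90 × 0.75 + 0.10 × r, where r is the rate at which the four are counted. Power uses the formula in step 1 with 40 per arm and ignores imputation uncertainty.

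| r | Difference | Power |
|---|---|---|
| 75% (as if at full week-4 response) | 42.0 points | 97.7% |
| 33% (roughly what Copy Reference would give) | 37.8 points | 93.8% |
| 0% (all non-responders at exit) | 34.5 points | 88.5% |

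Against Copy Reference, taking exit values as observed changes the difference by between 34.5 − 37.8 = −3.3 and 42.0 − 37.8 = +4.2 points.

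**The case against.** The strongest reply is that the protocol does not make early exit a week-4 visit. Only two list entries do so. The schedule of evaluations, the Visit 3 procedures and SAP 4.4 itself give day 28 ± 2 alone, and 6.3.2 describes a separate early termination visit. If the visit is recorded that way, the rule in SAP 4.4 keeps its data out of week 4, which is the desired result. The eCRF is not among the documents, so how sites record exits cannot be checked. This stands. A reader might infer that a day-10 value will enter the co-primary; the documents support only that it may.

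The affected group is also small. Patients who only stop treatment remain on schedule, and 6.3.1 asks for follow-up assessments unless consent is withdrawn. The 6.2 row for early termination lists no Schirmer test, although 6.3.2 implies one. This stands too.

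A reader might also infer that the rule credits cenegermin with on-treatment benefit, by as much as 4.2 points. That figure needs all 10% to leave before day 26, all with a Schirmer result, and all responding at the full 75%. The SAP's 10% is for patients not evaluable, with no timing given. Patients who leave for insufficient response are unlikely to respond at 75%. The comparison also leaves out vehicle exits and uses Copy Reference, which is the fallback to MI-RD. No direction is established.

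Blinded case-by-case review of deviations (SAP 8.2) and the per-protocol analysis may limit the effect. Neither says to which visit an exit value belongs.

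**Conclusion.** The concern holds as an unresolved inconsistency with a possible effect on a co-primary endpoint. The protocol gives conflicting places for early-exit data, and the SAP's nominal rule passes the conflict into the analysis. A Schirmer value from a patient who exits before day 26 may be analysed as observed at week 4. It would then avoid MI-RD or Copy Reference and the tipping-point shift, and could act as a donor that the SAP's text would exclude.

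The direct size is at most about 2.5 points in an arm's responder rate per affected patient, assuming about 40 per arm. The number of such patients, the direction of the shift and the size of any donor effect cannot be determined from the documents. The documents do not show that the error will occur or that it would favour cenegermin. It is still more than missing detail, because a stated rule combined with a stated visit definition can give a wrong endpoint value. It should be corrected before unblinding.

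**What to change.** 1. **Protocol:** reconcile the synopsis, the section 6 visit list, the Visit 7 row in 6.2 and the study-discontinuation text in 6.3.2, so that they agree on where early-exit data are recorded and whether the exit examination includes a Schirmer test.
2. **SAP 4.4:** state that early-termination assessments carry their own label. Assign one to a scheduled visit only if its study day (already defined in SAP 4.3) falls in that visit's protocol window, which for week 4 is day 26 to 30. Otherwise treat the scheduled endpoint as missing and impute it as in 10.1.2. Regular scheduled visits keep nominal assignment.
3. **SAP 15.4:** check that donor selection follows the text's definition of a retrieved drop-out once the labels are in place.

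The cost is a short SAP addition, one derivation from study day and a protocol clarification. The downside is a few more imputed values, and some real exit measurements not used as endpoint data. A day-10 value, for example, also falls outside the week-2 window of day 12 to 16. Such values can still be listed.

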#### 4.5 Baseline

Baseline is defined as the last visit prior to and including date of the randomization visit (Visit 1). Unless otherwise specified, baseline values are defined as the measurements taken during this visit. In case of multiple measurements during baseline visit, the last assessment will be considered as baseline evaluation before start of treatment.

#### 4.6 **Post-baseline**

For safety and efficacy evaluations all assessments after the first administration of study drug are considered as "post-baseline" assessment.

# 4.7 Eligible eye

Assuming that all the inclusion/exclusion criteria are met in both eyes, the worse eye (eligible eye) will be determined at the baseline visit using a stepladder approach, as follows:

- 1. Schirmer's Test: worse eye determined as eye with lower Schirmer I score.
- 2. NEI score: if Schirmer I score is the same in both eyes, worse eye will be determined by NEI score (cornea + conjunctival staining).

If all the above are identical, determination of the worse eye will be based on the investigator's judgement, otherwise the right eye will be used as the eligible eye.

# 5. Sample size justification

The sample size of the study is calculated based on results from previous studies.

Sample size was calculated according to the following assumptions:

- randomization ratio 1:1.
- a difference of 42% in Schirmer I rate of responders (value >10mm/5min at week 4.) in favor of rhNGF treatment at Week 4, with a responder rate of 33% for vehicle.
- 10 points in Global SANDE score improvement at Week 12, with a standard deviation of 12 points.

Based on these assumptions, a total sample size of 72 evaluable patients (80 pts considering 10% of patients not evaluable after enrollment) allows to achieve an overall power of 90% to show superiority of rhNGF eye drops solution vs vehicle in terms of primary endpoint, considering a one-sided alpha of 0.025.

Specifically:

- A power of 96.3% is achieved for Schirmer I primary endpoint.
- A power of 94.1% is achieved for SANDE primary endpoint.

